Lesions in the brainstem and deep brain locations are more likely than other CAs to bleed²¹, rebleed¹⁸, and cause severe disability^{19, 22}. It is unclear if this greater propensity to SH simply reflects the clinical impact of bleeds in those locations, while lesions in less eloquent brain regions may bleed at similar rates but more likely without symptoms. Per current clinical practice and evidence-based guidelines, CAs are typically observed expectantly, and surgically excised only *after significant clinical sequelae* (typically one or more hemorrhagic strokes) particularly in deep or brainstem locations^{17, 23}. Healthcare costs of hemorrhagic stroke can reach up to \$27,400/case in the first 90 days (2007 dollars), excluding socioeconomic impact of lost productivity²⁴.

While brain surgery for lesion excision may benefit some patients, it can be associated with significant cost and morbidity. It is expensive, with a typical craniotomy costing \$37,438 in 2011 dollars²⁵, excluding the cost of complications. More concerning are complications and morbidity with CA surgical excision, particularly with brainstem lesions, associated with a particularly alarming rate of surgical adverse events²³. In a non-randomized population-based cohort study, lesion excision was associated with significantly worse functional outcomes and greater complications compared to conservative management²³. Stereotactic radiosurgery has been proposed but there is controversy about its effectiveness and concern about complications and radiation-induced genesis of new CAs^{26, 27}.

The rates of development of new lesions, and of first SH in asymptomatic CAs, are far too low to allow meaningful testing or to compel primary prevention strategies for CASH. Cases with recent SH, where surgical resection is not undertaken (mostly in deep and brainstem locations), are the most likely to be followed expectantly per current evidence based guidelines¹⁷, with clinical equipoise for testing novel therapies aimed at preventing re-bleeding. It would be desirable to develop a drug that stabilizes CASH, and prevent recurrent bleeding. It would mitigate neurologic sequelae of re-bleeds and the complications of surgical resection in many patients. Based on current knowledge of natural history, the

likelihood of therapeutic benefit for secondary prevention (symptomatic re-bleed) would be greatest within 2-3 years after a SH¹⁷⁻¹⁹.

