4.3 END OF STUDY DEFINITION

A participant is considered to have completed the study if he or she has completed all phases of the study including the last visit or the last scheduled procedure shown in the Schedule of Activities (SoA), Section 1.3.

Cases whose CASH lesion has been resected will be considered to have reached endpoint, and will not be followed further during the study. The indication for surgery shall be noted, including any SH prior to CASH lesion resection.

Cases who develop a recurrent SH during follow-up, and their CASH lesion has not been excised, will remain in the study until they complete follow- up, and will undergo all scheduled assessments.

If an enrolled subject decides to discontinue the study, fails follow-up, or develops an exclusion criterion after enrollment in the study (becomes pregnant, undergoes CASH lesion excision, etc.), he/she will be considered an attrition after recording the causative event. Data collected prior to the attrition shall still be included in the study and no further patient follow-up will take place. An allowance in sample size calculation is made for up to 30% attrition or missing data from any cause.

5 Study Population

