Specific Aim 3. Time to recurrent SH will be analyzed using Kaplan Meier method and Cox proportional hazards regression approach. Rates of recurrent SH/patient/year from initial SH qualifying event, and SH/patient/year from enrollment (potentially more relevant for trial modeling) will be estimated along with 95% CIs. Changes in mean lesional QSM and K_i during 1 and 2-year epochs will be compared using paired t-test or Wilcoxon signed rank test to assess changes within patients over time, including 95% CIs. To test predictive, monitoring or surrogate outcome hypotheses, two sample t-test or Wilcoxon rank sum test will be used to compare such changes between patients with and without recurrent SH. Categorical variables such as proportions of patients with a drop in mRS score ≥ 1 point, difference in EQ-5D and PROMIS 29 scores, NIHSS scores, between patients with and without recurrent SH will be compared using Chi-square or Fisher's exact test. Associations of baseline characteristics (sex, lesion locations, familial/sporadic) and recurrent SH as a binary outcome (yes/no) will be assessed using

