Follow-up and Biomarker Validation (FUBV) Sites: University of Chicago, University of New Mexico, Mayo, University of California San Francisco, and Johns Hopkins were chosen because of additional established infrastructure for advanced imaging, including identified MRI physicists, neuroradiologists and site engineers who will work with the Biomarker Imaging Core (BIC) on implementing QSM and DCEQP protocols. A subset of approximately 120 CASH cases will be enrolled at FUBV sites to perform imaging biomarker validation studies (Specific Aim 2) and follow-up of CASH cases annually for up to two years (Specific Aim 3) to evaluate changes in outcomes. This subset of CASH cases will undergo a research MRI scan at baseline and at 1 and 2-year follow-up visits and undergo modified Rankin Scale (mRS) score and EQ-5D, PROMIS 29, and NIHSS assessments. A target recruitment of 120 CASH cases over 3-4 years at the sites conducting the FUBV arm is amply justified, with demonstrated 256 CA cases recently evaluated per year at those sites, expecting to identify 38 CASH cases each year (15% prevalence). Utah and Barrow may also serve as alternate FUBV arm sites if needed, with large demonstrated CA clinical activity. The University of California San Francisco and Johns Hopkins are now part of the FUBV arm.

Assuming a sample size of 120 CASH cases, and allowing 30% dropouts or missing biomarker or other data, we would have 84 evaluable patients (168 patient-years). We project 10%-20% re-bleed rate/year, supported by population studies and meta-analyses of CASH^{18, 19}, with the higher estimate particularly applying to brainstem cases. We would hence expect 17-34 SHs. Based on this, for continuous outcomes we will have 80% power at an alpha level of 0.05, to detect a difference between the means of patients with and without re-bleeding of at least 0.63-0.77 standard deviation. For categorical outcomes (i.e. presence or absence of a risk factor) we will be able to detect a difference of 32-40% between these two groups. This allows testing of questions regarding the rate of SH, and the prevalence of other outcomes in relation to SH during follow-up (Specific Aim 3).

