Predictors of SH: Two sample t-test or Wilcoxon rank sum test will be used to compare such changes between patients with and without recurrent SH. Categorical variables such as proportions of patients with a drop in mRS score ≥ 1 point, between patients with and without recurrent SH will be compared using Chi-square or Fisher's exact test. Associations of baseline characteristics (sex, lesion locations, familial/sporadic) and recurrent SH as a binary outcome (yes/no) will be assessed using univariable and multivariable logistic regression and reported as odds ratios and 95% CIs. Depending on the number of recurrent SH over the 2-year period, we may analyze re-bleeds as a continuous outcome and the associations of baseline features or biomarkers assessed using linear regression. Performance of final model(s) will be assessed using r^2 in the case of linear regression, area under the curve (AUC) and Hosmer Lemeshow goodness of-fit test⁵⁵ in the case of logistic regression, or concordance index in the case of Cox proportional hazards regression. AUCs between various models (univariable) will be compared using the method proposed by DeLong et al⁵⁶. For biomarkers, we will create a binary variable (yes/no) depending on whether the % change in mean lesional QSM or K_i during 1-year epochs exceed previously defined respective thresholds (+ 5.8% QSM and +39.6% for K_i) that were significantly associated with new clinical events at high sensitivity and specificity in previously stable lesions³³. We will then assess the association of this newly created variable ("biomarker event") with SH rate treated as both continuous (using two sample t-test or Wilcoxon rank sum test) and binary (using Chi-square or Fisher's exact test) outcomes of interest. Finally, we shall compare the sensitivity/specificity of changes in mRS, QOL, and NIHSS scores, and lesional QSM and K_i in relation to SH during the same epochs, using McNemar's test with SH (yes/no binary) as the reference standard. All tests will be two-sided and p-values <0.05 considered statistically significant.

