9.4.2 SUB-GROUP ANALYSES

All endpoints (rebleed rates, biomarker changes, functional status and QOL changes) shall be analyzed by pre-defined subgroups (sex, genotype and lesion location), information which may influence stratification or the need for adaptive randomization in clinical trials.

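### Baseline predictors of recurrent symptomatic hemorrhage are assigned to logistic regression on a yes/no outcome, which distorts the odds ratio if hemorrhage-free exit differs by the predictor; the planned Cox model should be named instead

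*Combined protocol and SAP*

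**What the plan says.** Two analyses of recurrent SH sit side by side in sections 9.1 (Specific Aim 3) and 9.4.1.

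- **Event rate:** "Time to recurrent SH will be analyzed using Kaplan Meier method and Cox proportional hazards regression approach". SH per patient-year, with 95% CIs, is estimated as well. No covariates are named.
- **Baseline predictors** (sex, lesion location, familial/sporadic): "recurrent SH as a binary outcome (yes/no) will be assessed using univariable and multivariable logistic regression and reported as odds ratios and 95% CIs". No person-time offset, fixed risk window or coding rule for a patient who leaves SH-free is given.

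Cox appears again in the predictor text, but only as a conditional performance measure: "concordance index in the case of Cox proportional hazards regression". Section 9.4.2 adds: "All endpoints (rebleed rates, biomarker changes, functional status and QOL changes) shall be analyzed by pre-defined subgroups (sex, genotype and lesion location"), without naming a model.

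On follow-up, section 9.2 plans "follow-up of CASH cases annually for up to two years" in about 120 patients. Section 4.3 stops follow-up at resection, keeps what was collected before any exit, and states: "An allowance in sample size calculation is made for up to 30% attrition or missing data from any cause". Sections 4.3 and 7.1 describe a resected case as having arrived at an endpoint; sections 4.3 and 7.2 also class excision of the lesion as attrition.

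**The concern.** A patient who leaves SH-free at month 3 and one followed SH-free for 24 months can carry the same value in a yes/no outcome. This does no harm under the null if early exit is unrelated to the predictor. Lesion location might be related to it. Section 2.2 describes the group left for expectant management as "Cases with recent SH, where surgical resection is not undertaken (mostly in deep and brainstem locations"), and resection is one of the events that ends observation. The odds ratio for location could then partly reflect time under observation.

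The coding of SH-free exits is also open, and it decides the direction of any distortion. Leaving it open allows the choice to be made after the data are seen.

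Section 9.3 intends the models of recurrent SH to inform covariate-adaptive randomization in a Phase III trial, so a spurious or missed predictor could carry over into that design.

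**Working it through.** **The plan's own figures (section 9.2).** 120 × 0.70 = 84 evaluable patients; 84 × 2 = 168 patient-years; 168 × 0.10 = 16.8 and 168 × 0.20 = 33.6, matching 17 to 34 SHs. A two-sided t-test with 80% power gives 0.77 SD (17 v 67) and 0.63 SD (34 v 50), as stated. The plan gives no figure for an odds ratio or its bias.

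**Inputs.** From the documents: SH rate h = 0.10 to 0.20 per year, two years of follow-up, up to 30% attrition or missing data, 120 patients. Assumed: two equal groups, constant rates, exits uniform over two years, and an exit split of 15% v 45% (mean 30%). The split is an assumption; the documents give only the total.

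**Exits counted as no SH.** With exit fraction a,

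P(SH seen) = (1 − a)(1 − e^(−2h)) + a[1 − (1 − e^(−2h))/(2h)].

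At h = 0.15, 1 − e^(−0.30) = 0.259 and the bracketed term is 0.136.

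- a = 0.15: 0.85 × 0.259 + 0.15 × 0.136 = 0.241, odds 0.317
- a = 0.45: 0.55 × 0.259 + 0.45 × 0.136 = 0.204, odds 0.256
- Odds ratio, longer-followed v early-exit: 0.317/0.256 = 1.24. True value: 1.00.

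| Exit split, no true effect | h = 0.10 | h = 0.15 | h = 0.20 |
|---|---|---|---|
| 30% v 30% | 1.00 | 1.00 | 1.00 |
| 7.5% v 22.5% | 1.10 | 1.11 | 1.11 |
| 15% v 45% | 1.22 | 1.24 | 1.26 |

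Read the other way, the early-exit group's odds ratio at 15% v 45% is the reciprocal, 0.80 to 0.82.

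**SH-free exits dropped, exits after SH kept.** The odds become P(SH seen)/[(1 − a)e^(−2h)]. At h = 0.15, e^(−0.30) = 0.741:

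- a = 0.15: 0.241/(0.85 × 0.741) = 0.382
- a = 0.45: 0.204/(0.55 × 0.741) = 0.500
- The early-exit group's odds ratio is now 0.500/0.382 = 1.31, so the direction has reversed.

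**A true difference, 20% v 10% per year, exits counted as no SH.**

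- Full follow-up: probabilities 0.330 and 0.181, odds 0.492 and 0.221, odds ratio 2.22.
- Higher-risk group stays longer (15% v 45%): probabilities 0.307 and 0.142, odds ratio about 2.67.
- Higher-risk group exits early (45% v 15%): probabilities 0.260 and 0.168, odds ratio 1.74.

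**False positives.** Simulation with 60 per group, no true effect and 20,000 runs per setting gives a two-sided rejection rate of about 6 to 8% at 15% v 45%. The events-per-person-time rate ratio stays near 1.0 with 4 to 5%. The upper-to-lower ratio of the 95% CI for the odds ratio is about 5 to 8.

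**The case against.** The strongest defence is that methods using follow-up time are already in the plan: Kaplan-Meier, Cox, SH per patient-year, a concordance index, and rebleed rates by sex, genotype and location. That stands in part. It shows that event and exit times must be available and makes the repair small. It does not replace the sentence that assigns these predictors to logistic regression.

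The driver is also uncertain, and this stands. No exit figures by location are given. The 30% includes missing data, and a missing scan does not shorten SH follow-up. Eligibility (section 5.2) appears meant to keep out patients with planned treatment, which would limit early resection. Section 2.2 describes which patients go unresected in general, not who is resected after enrollment, and it also links excision after serious sequelae to deep and brainstem lesions. Any SH before resection is recorded, so exits after an SH do not bias a first-SH analysis.

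Four stronger readings are tempting, and the documents support none of them:

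- *A predictor linked to early exit has its odds ratio inflated.* With exits counted as no SH, it is lowered; the comparison group is inflated.
- *At a true rate ratio of 2.0, an odds ratio of 2.67 is all bias.* Full follow-up already gives 2.22, because an odds ratio is not a rate ratio. Differential exit accounts for the step from 2.22 to 2.67.
- *Only completers will be coded.* Section 4.3 keeps data collected before exit.
- *These odds ratios alone will pick the Phase III factors.* Section 9.3 refers to models in general, and section 9.4.2 gives subgroup rebleed rates the same purpose.

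**Conclusion.** The concern holds as a conditional one. The only method explicitly tied to the baseline predictors ignores unequal follow-up and leaves the coding of SH-free exits open. Distortion under the null requires SH-free exit to differ by the predictor, and its direction depends on the coding.

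Under the assumed 15% v 45% split, a null odds ratio becomes 1.22 to 1.26 (1.10 to 1.11 at 7.5% v 22.5%), and 2.22 becomes about 2.67 or 1.74 depending on which group leaves early. With 17 to 34 expected SHs, sampling error is larger than this. Severity is moderate: worth correcting because it is cheap and removes a choice that could be made after the data are seen, but not a flaw that invalidates Aim 3.

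**What to change.** In sections 9.1 and 9.4.1:

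1. Name the Cox model already planned as the main model for baseline predictors: time from enrollment to first recurrent SH, censored at exit, reported as hazard ratios with 95% CIs and the concordance index.
2. State whether the analysis treats resection as censoring or as a competing event, and reconcile the two descriptions of a resected case (endpoint in 4.3 and 7.1, attrition in 4.3 and 7.2).
3. Keep logistic regression only as a secondary analysis, with a fixed window and a stated rule for patients who exit before the window closes.

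Firth penalisation for sparse location categories is optional and a separate matter.

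The cost is SAP wording; the planned Kaplan-Meier analysis already needs the SH and exit dates. The small downside is that censoring at resection assumes resection is uninformative given the covariates, and the SAP should say so.

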Years 3-4	
Publish guidelines paper on reporting Terminology in CAs by the end of year 3.Screen at least 50 cases/year, enroll 10 CASH cases/year at each SCA/FUBV site.Log follow-up at least 40 cases/year for sites participating in the FUBV arm by the end of year 3 and 60 cases by the end of year 4 with clinical and biomarker data.Confirm quality and consistency of harmonized data acquisitions across sites at the end of years 3 and 4.Complete lagging enrollments and follow-ups.Test hypotheses regarding relative value/sensitivity of outcomes instruments.Apply for certification of 1 or more outcomes instruments by the FDA.Formulate trial hypotheses.	
Decision regarding certifiable outcomes based on interim and/or final analyses of trial readiness aims (SH alone, versus QOL and biomarkers); application to FDA.Decision regarding # of subjects (and # of sites) needed for clinical trials, including stratification and outcome parameters.Decisions regarding multi-site trial models per results of readiness aims. Pharma, StrokeNet and NCATS consultations.
Year 5 (6)		

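### The head-to-head of outcome instruments against SH rests on unmatched and partly unstated cut-offs, so a McNemar difference is not by itself a difference in discrimination

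*Combined protocol and SAP*

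**What the plan says.** Section 9.4.1 (Predictors of SH), in text that section 9.1 also carries under Specific Aim 3, ends with a head-to-head of the instruments. It will "compare the sensitivity/specificity of changes in mRS, QOL, and NIHSS scores, and lesional QSM and K_i in relation to SH during the same epochs". The test named is McNemar's, and SH, taken as present or absent, is the reference.

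The documents supply these cut-offs for change:

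- **QSM and K_i:** "thresholds (+ 5.8% QSM and +39.6% for K_i"), applied to 1-year epochs. They come from earlier work, where they were "significantly associated with new clinical events at high sensitivity and specificity in previously stable lesions". They define the binary biomarker event, and the text does not expressly assign them to the McNemar step.
- **mRS:** "proportions of patients with a drop in mRS score ≥ 1 point", given for a chi-square or Fisher comparison and not for the McNemar step.
- **EQ-5D, PROMIS 29, NIHSS:** none. Section 9.1 lists "difference in EQ-5D and PROMIS 29 scores, NIHSS scores, between patients with and without recurrent SH" among the categorical variables without saying how a score difference becomes a category. The SD bands for QOL in sections 9.1 and 9.4.1 grade the level of a score against a reference mean, not its change.

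Section 9.4.1 also names a method that needs no cut-off: "AUCs between various models (univariable) will be compared using the method proposed by DeLong et al". The predictors named for the logistic models are baseline characteristics; biomarkers are mentioned only for the optional linear model.

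The milestones table in section 10.1.2 includes "Test hypotheses regarding relative value/sensitivity of outcomes instruments", next to an application to the FDA for certification of instruments. Section 4.2 lists as a knowledge gap whether the biomarkers respond more sensitively than clinical events do.

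**The concern.** Sensitivity and specificity belong to an instrument together with a cut-off. Loosening the cut-off raises sensitivity and lowers specificity without changing how well the instrument separates patients with SH from those without. If two instruments are cut at different specificities, McNemar's test among SH patients can favour one and McNemar's test among SH-free patients the other, and that pattern is expected even when the two are equally good.

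There is a second problem for EQ-5D, PROMIS 29 and NIHSS. As written, their part of the comparison cannot be run until someone chooses a cut-off and a direction of change, and nothing requires that choice to come before SH data are seen. Section 10.1.5 has the Executive Committee reviewing interim analyses yearly.

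The stake is the choice of outcome for later trials. A ranking that came from the cut-offs would feed the decision in section 10.1.2 between SH alone and QOL or biomarker outcomes.

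**Working it through.** **1. The plan's own figures (section 9.2).** 120 × (1 − 0.30) = 84 evaluable patients; 84 × 2 = 168 patient-years; 168 × 0.10 = 16.8 and 168 × 0.20 = 33.6, matching the stated 17–34 SHs. A two-sample t-test at 80% power and two-sided 0.05 gives a detectable difference of 0.770 SD (17 v 67) and 0.630 SD (34 v 50), as stated. With a continuity correction and a comparison rate of 30%, the detectable difference in proportions is 0.400 and 0.329, in line with the stated 32–40%. No power or precision is given for the sensitivity/specificity comparison.

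**2. Equal instruments, different cut-offs.** The documents give no expected AUC, sensitivity or specificity for any instrument, so the values here are assumptions. For a binormal score with equal variances, d = √2 × z(AUC) and sensitivity = Φ(d − z(specificity)). At AUC 0.75, d = 1.414 × 0.6745 = 0.954.

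- Specificity 0.90: Φ(0.954 − 1.282) = 0.372.
- Specificity 0.70: Φ(0.954 − 0.524) = 0.666.

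The gap is 29 points with identical discrimination. Over a range of AUC:

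| AUC | Sensitivity at specificity 0.70 | Sensitivity at specificity 0.90 | Gap |
|---|---|---|---|
| 0.70 | 0.586 | 0.295 | 0.291 |
| 0.75 | 0.666 | 0.372 | 0.294 |
| 0.80 | 0.747 | 0.464 | 0.283 |
| 0.90 | 0.901 | 0.702 | 0.199 |

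**3. What McNemar's test then reports.** Two instruments with the same AUC (0.70, 0.80 or 0.90), correlation 0.3 (assumed), 84 patients of whom 17 or 34 have SH, exact McNemar on sensitivity, 3,000 simulated studies per setting:

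| Specificities of the two cut-offs | Significant, 17 SH | Significant, 34 SH |
|---|---|---|
| 0.80 and 0.80 | 0.3–1.5% | 1.8–3.2% |
| 0.70 and 0.90 | 12–30% | 47–66% |
| 0.60 and 0.95 | 60–83% | 97–99.5% |

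Matched cut-offs keep the error below 5%; unmatched ones do not. A worse instrument can also win on sensitivity. With AUC 0.75 cut at specificity 0.60 (sensitivity 0.76) against AUC 0.85 cut at 0.95 (sensitivity 0.43), the worse one is significantly more sensitive in 39% of studies with 17 SH and 80.5% with 34, while specificity almost always points the other way.

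**4. Cut-offs tuned to the data.** Take a continuous score unrelated to SH and cut it where sensitivity + specificity − 1 (the Youden index) is largest. Over 3,000 simulated studies of 84 patients the mean index is about 0.13 (34 v 50) and 0.15 (17 v 67), where the truth is 0. For a coarse score with half the patients assumed unchanged, as NIHSS change might be, it is about 0.07 and 0.09.

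Steps 3 and 4 count each patient once, whereas the plan compares by epoch.

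**The case against.** Four points on the other side carry weight.

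- **Fixed rules are worth comparing.** A later trial might use the biomarker event exactly as defined, and asking how that rule performs is legitimate. If one instrument is better on both sensitivity and specificity, the comparison does rank the two at those operating points. A reader might infer that the planned comparison can never show which instrument detects SH best. That goes too far: it is ambiguous only when the two measures disagree.
- **The plan already has cut-off-free analyses.** Section 9.4.1 compares the change scores between patients with and without SH by t-test or rank-sum test, and the rank-sum statistic is a rescaled AUC. This assesses each instrument separately; it is not a paired comparison of two. The DeLong sentence does not exclude change scores, but no sentence applies it to them.
- **Post-hoc cut-offs are a risk, not a fact.** A reader might infer that the QOL and NIHSS cut-offs will be chosen with SH status known. Section 10.1.4 has the statisticians refining the plans in year 1, and section 4.1 puts data collection in years 2–5, so they could be fixed in time. Nothing there promises it.
- **It is not an endpoint.** A reader might take the head-to-head as the answer to Aim 3. Section 3 states that aim as SH rates and changes in biomarkers, function and QOL, and the synopsis lists no instrument comparison among the endpoints. Its support is the gap named in section 4.2 and the milestone in section 10.1.2.

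**Conclusion.** The concern stands in this form: cut-offs for change in EQ-5D, PROMIS 29 and NIHSS are not given, and those for QSM, K_i and mRS are not matched on specificity, so a McNemar difference in sensitivity or specificity is not a difference in discrimination unless one instrument is better on both. Writing down the missing cut-offs would not be enough, because fixed but unmatched cut-offs still allow equal instruments to differ significantly.

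The size depends on assumptions. Equal binormal instruments with AUC 0.70–0.90, cut at specificities of 0.70 and 0.90, differ by about 20 to 29 points in sensitivity; tuning a cut-off adds up to about 0.15 to the Youden index of a useless continuous score, and roughly half that for a coarse one. Only the patient and event numbers are the plan's. The actual specificities of the +5.8%, +39.6% and one-point rules in this cohort are unknown. The biomarker thresholds also come from lesions that had been stable, whereas these patients bled within the past year.

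This should be changed before the comparison is run. It does not affect the SH rate or the other listed endpoints.

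**What to change.** In sections 9.1 (Specific Aim 3) and 9.4.1:

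1. Make the main head-to-head the paired difference in AUC of the change scores against SH in the same epoch and the same patients. Treat EQ-5D and each PROMIS 29 domain as separate instruments.
2. Take confidence intervals from a patient-level bootstrap or a clustered version of DeLong's method. The standard DeLong method does not allow for two epochs from one patient.
3. Keep McNemar's test as secondary, only for rules whose cut-off and direction of change are written down before SH data are seen. State the direction for mRS too, since a drop could mean a lower score or a worse state. Say whether the QSM, K_i and mRS cut-offs are the ones to be used here.
4. Report sensitivity and specificity jointly for each rule, and claim superiority only when both favour the same instrument.

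Sensitivity at one common specificity is less suitable as the main measure: integer scores such as mRS and NIHSS will generally not reach a chosen specificity without interpolation, and each cut-off would have to be estimated from 50 to 67 SH-free patients.

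The cost is SAP wording and a little more analysis; no new data are needed. The downside is that AUC does not evaluate a fixed decision rule, which the secondary McNemar analysis still covers.
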